8.3. Additional Evaluations

8.3.1. Meniere's Symptom Questionnaire

The Meniere's symptom questionnaire is a set of questions that will be administered at Study Visits 1, 2, and 3. Each question has 5 possible responses: 1) No Vertigo/No Tinnitus/No Ear Fullness/No Hearing Difficulty (depending on the question administered), 2) Mild, 3) Moderate, 4) Severe, and 5) Extremely Severe. This assessment is considered an additional endpoint.

9. ADVERSE EVENT (AE) REPORTING

Timely, accurate, and complete reporting and analysis of safety information from clinical trials will be conducted in accordance with Good Clinical Practice.

All AEs, including SAEs reported or observed during or after dosing with the study drug will be recorded on the AE page of the eCRF for all enrolled subjects. Information to be collected includes description of event, date of onset, investigator-specified assessment of the severity and relationship to study drug, date of resolution of the event, seriousness, any required treatment or evaluations, and outcome. Adverse events resulting from concurrent illnesses, reactions to concurrent illnesses, reactions to concurrent medications, or progression of disease states must also be reported. Perforations of the tympanic membrane will be captured as AEs only if the perforation increases in size and does not resolve by the end of the study.

If the existing medical condition worsens at any time after application of study drug, it should be recorded as an AE.

9.1. Adverse Event Classification Definitions

Adverse Event:

An AE is any unfavorable and unintended diagnosis, symptom, sign, syndrome or disease which occurs during the study, having been absent at baseline, or, if present at baseline, appears to worsen.

This includes any occurrence that is new in onset or aggravated in severity or frequency from the baseline condition, including abnormal results of diagnostic procedures and/or laboratory test abnormalities, which are considered AEs if they:

- result in discontinuation from the study
- require treatment or any other therapeutic intervention
- require further diagnostic evaluation (excluding a repetition of the same procedure to confirm the abnormality)
- are associated with clinical signs or symptoms judged by the investigator to have a significant clinical impact

Serious Adverse Event (SAE):

An SAE is defined as any untoward medical occurrence that:

- results in death,
- is life-threatening (Note: the term "life-threatening" refers to an event in which the subject was at risk of death at the time of the event rather than to an event which hypothetically might have caused death if it were more severe.),
- requires in-patient hospitalization or prolongation of existing hospitalization,
- results in persistent or significant disability/incapacity, or
- is a congenital anomaly/birth defect.

Medical and scientific judgment should be exercised in deciding whether expedited reporting is appropriate in other situations, such as important medical events that may not be immediately life-threatening or result in death or hospitalization but may jeopardize the subject or may require intervention to prevent one of the other outcomes listed in the above definition. These events should be considered serious.

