6.2. Compliance

OTO-104 will be administered by site personnel as a single, intratympanic injection at Visit 1 and 2 except when withheld due to potential safety concerns. Any deviations in administration will be documented in the source documents and the eCRF.

The site will maintain a log of all study drug dispensed and returned. Drug supplies for each subject will be inventoried and accounted for throughout the trial.

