10.2.1. Handling of Withdrawals

Subjects will be free to withdraw from further study drug administration and further follow-up the study at any time. Subject participation in the study may be stopped at any time at the discretion of the investigator or at the request of the sponsor.

Whenever possible, all subjects who withdraw from further study drug administration should be encouraged to remain on-study for further follow-up through the subject last scheduled visit. However, should a request for early withdrawal from the study with no further follow-up be made, the subject should be encouraged to return to the study site for a last follow up visit and undergo all end of study/early termination assessments.

When a subject withdraws from further administration of study drug or the study prior to completing Visit 3 (Month 6), the reason for withdrawal is to be documented on the eCRFs and in the source document.

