14.7. Data and Safety Monitoring Plan

The sponsor shall promptly review all information relevant to the safety of the drug obtained or otherwise received from foreign or domestic sources, including information derived from this clinical study and any other clinical study conducted with OTO-104. In order to comply with this, the sponsor and CRO medical personnel will have the ability to review safety information as it is entered and verified in the electronic data capture system (Section 14.5). Depending on the enrollment rate, all AEs in the ear and labyrinth disorders SOC will be reviewed at least every other month. In addition, reasons for study discontinuation will be reviewed to see if any trends in study discontinuation are identified.

Investigators are instructed to contact the Product Safety within 24 hours following the identification of a SAE (Section 9.2.2). All SAEs will be reviewed by the sponsor and CRO medical personnel within 1-2 days after receipt whether or not the event was considered associated with study drug. The sponsor assumes responsibility for appropriate reporting to the regulatory authorities. The investigator assumes responsibility for reporting events to the REC in accordance with the REC requirements. All SAE's will be part of the CRO medical personnel/sponsor safety review.

If, through this ongoing review, the sponsor determines that OTO-104 presents an unreasonable and significant risk to subjects, the sponsor shall take appropriate steps to suspend or discontinue the study and notify regulatory authorities, investigators and RECs as appropriate.

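### Section 9.1 makes a test abnormality an AE if the subject leaves the study because of it, but not if the second injection is withheld and the subject stays, so some dose-limiting findings can be missing from the TEAE tables

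*Combined protocol and SAP*

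**What the plan says.** The sole objective (Section 2) is the safety of repeat intratympanic injections, and each subject has at most two, at Day 1 and Month 3 (Section 3).

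After a general definition of an AE, Section 9.1 says when abnormal diagnostic or laboratory results are AEs. There are four alternatives. The results:

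- "result in discontinuation from the study";
- "require treatment or any other therapeutic intervention";
- need further diagnostic evaluation, where merely repeating the same test does not count;
- "are associated with clinical signs or symptoms judged by the investigator to have a significant clinical impact".

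On dosing, 6.2 says the injection is given at Visits 1 and 2 "except when withheld due to potential safety concerns", and that deviations in administration go in the source documents and the eCRF. On follow-up, 10.2.1 says that, whenever possible, "all subjects who withdraw from further study drug administration should be encouraged to remain on-study for further follow-up"; 10.2 says much the same.

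The items to be collected for each AE under Section 9 run from the description of the event to "any required treatment or evaluations, and outcome". Section 9.2.1 repeats them. Neither list names the action taken with study drug. Section 11.7.1 makes TEAEs the primary AE analysis and plans a listing of AEs that led to study withdrawal. Section 14.7 says "reasons for study discontinuation will be reviewed to see if any trends in study discontinuation are identified".

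**The concern.** The protocol treats stopping drug and leaving the study as separate events, and prefers that a subject who stops drug stays. The AE rule for test results recognises only the second event. Whether a given finding is an AE can then depend on what the subject does next rather than on the finding.

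This matters because a second injection withheld for safety bears directly on the only question the study asks. If the finding behind it is not an AE, it does not count towards TEAE incidence and cannot appear in an AE listing. Even when the finding is recorded as an AE, the stated AE items do not tie it to the missed injection.

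**Working it through.** No arithmetic applies, and the plan gives no figure to reproduce. The check sets the sections side by side.

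**1. Can a test result be known before the second injection?** Yes. Section 8.1.2 puts audiometry, tympanometry and otoscopy at Visit 2 ahead of dosing.

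**2. Can that result stop the injection while the subject stays?** Yes. Section 6.2 allows withholding for safety, and 10.2 and 10.2.1 encourage continued follow-up. Table 1, footnote 6, makes the same separation for pregnancy: no further dosing, but follow-up is completed. (Pregnancy has its own reporting route in 9.2.3 and is not part of this gap.)

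**3. Does any 9.1 condition cover it?** Of the four, one refers to discontinuation from the study and none to study drug being withheld or stopped. Take a new, asymptomatic tympanogram change at Month 3 with no diagnosis, no treatment and no work-up beyond a repeat test:

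| 9.1 condition | Subject leaves because of it | Second injection withheld, subject attends Month 6 |
|---|---|---|
| Discontinuation from the study | met | not met |
| Treatment or intervention | not met | not met |
| Further evaluation beyond a repeat | not met | not met |
| Signs or symptoms of significant impact | not met | not met |
| AE under the test-result rule | yes | no |

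Withholding a drug is not naturally read as a therapeutic intervention, so the second condition does not fill the gap.

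**4. Does Section 9 fill it?** Only in part. Section 9 makes worsening of an existing condition an AE. An audiogram shift in the affected ear might be recorded that way, since hearing loss belongs to the disease. A new tympanogram finding would not be. Perforations have their own rule in 8.2.5 and Section 9 and are left out here.

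**5. Where does the finding appear?** In the test summaries: otoscopy (11.7.3), audiometry (11.7.4) and tympanogram shifts (11.7.5). None of these is planned by whether the second injection was given. The missed injection and the reason for withdrawal from drug are provided for on the eCRF (6.2, 10.2.1). Section 11 leaves detail to the SAP, which could add listings, but an AE listing cannot show an event that was never entered as an AE.

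**The case against.** The case against is substantial, and it narrows the point.

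- **The list is not exclusive.** A reader might infer that test results are AEs only on these four conditions. Section 9.1 says that they are AEs if a condition is met, not only if. The general definition covers any new unfavourable sign or diagnosis, so a new tympanic-membrane change seen by the physician could qualify directly. Section 9.2.1 asks for diagnoses where possible, so a tympanogram read as middle ear effusion would also qualify. This stands. It leaves the isolated test value with no diagnosis, for which the four conditions are the only specific rule.
- **The information is kept.** A reader might infer that a withheld injection is recorded only as a dosing deviation. Section 10.2.1 also requires the reason for withdrawal from drug on the eCRF, although its wording has the subject withdrawing and fits an injection withheld by the investigator less clearly. The test summaries show the finding in any case. What is at risk is the TEAE count and the link to dosing.
- **The sponsor can still see it.** A reader might infer that a cluster of withheld injections would escape review. Section 14.7 commits the sponsor to reviewing all safety information and gives sponsor and CRO medical staff access as data are entered. The discontinuation review is additional. What stands is narrower: neither of the specific reviews named there, of ear and labyrinth AEs and of discontinuation reasons, is directed at injections not given.
- **Section 10.1 counts subjects who stop drug as non-completers**, so some sites may read the first condition as covering them. Section 10.2.1 names drug and study withdrawal separately, which weighs against that reading. Across 60–70 sites the ambiguity invites uneven reporting.
- **An action-taken field may exist.** Section 9.2.1 requires measures for AE management to be recorded, and refers to eCRF guidelines that are not in these documents. The lists in 9 and 9.2.1 omit the item; that the eCRF lacks it is not shown.

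**Conclusion.** The gap is real but narrow. As written, 9.1 can leave out of the TEAE tables an isolated Month 3 test abnormality that ends repeat dosing in a subject who stays in follow-up, while counting the same abnormality in a subject who leaves. It is a shortfall in AE classification, not a loss of data.

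Its size is unknown and probably small. The documents give no rate of withheld second injections, and many findings serious enough to stop dosing will meet another condition or the general definition. A reader might want a count: an assumed 2–5% of the maximum 300 subjects would be 300 × 0.02 = 6 to 300 × 0.05 = 15. Nothing in the documents supports that rate for findings that meet no other condition, so it should not be taken as an estimate. A reader might also infer that AE incidence in general falls as retention improves. That could hold only within this residual group.

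The conclusion rests on reading withdrawal from drug and discontinuation from the study as different events, as 10.2.1 does. The correction is worth making because repeat-dose safety is the only objective and the change is small.

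**What to change.** Four matching edits:

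1. In 9.1, change the first condition to: *result in study drug being withheld or discontinued, or in discontinuation from the study*.
2. In 9 and 9.2.1, add action taken with study drug (given, withheld, discontinued) to the items recorded for each AE.
3. In 11.7.1, extend the listing of AEs leading to study withdrawal to those leading to a withheld or discontinued injection.
4. In 14.7, name the reasons for a second injection not given in the trend review.

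The cost is one phrase, one eCRF item if it is not already there, one wider listing and one added line in an existing review. The AE count will be slightly higher. These edits govern recording and reporting only; they do not affect when an injection is given or withheld.

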9.1.1. Assessment of Severity

The investigator will assess the intensity of the AE and rate the AE as mild, moderate, or severe using the following criteria:

Grade 1 – Mild: These events are easily tolerated, require minimal or no treatment, and do not interfere with the subject's daily activities.

Grade 2 – Moderate: These events cause sufficient discomfort to interfere with daily activity and/or require a simple dose of medication, e.g., analgesics or anti-emetics.

Grade 3 – Severe: These events incapacitate and prevent usual activity or require complex medication/treatment or hospitalization.

Grade 4 – Life Threatening: These events are those for which the subject was at risk of death at the time of the event rather than an event which hypothetically might have caused death if it were more severe.

Grade 5 – Death: The event resulted in the death of the subject.

Changes in the severity of an AE should be documented to allow for an assessment of the duration of the event at each level of intensity to be performed.

9.1.2. Assessment of Causality

The investigator's assessment of an AE's relationship to study drug will be part of the documentation process, but will not be a factor in determining what is or is not reported in the study.

The investigator will assess the relationship or association of the study drug in causing or contributing to the AE, which will be characterized using the following classification and criteria:

Definite: Adverse events that, after careful medical evaluation, are considered definitely related to the study drug; other conditions (concurrent illness, progression/expression of disease state, or concurrent medication reaction) do not appear to explain the event.

Probable: Adverse events that, after careful medical evaluation, are considered with a high degree of certainty to be related to the study drug. The following characteristics will apply:

- a reasonable temporal relationship exists between the event and exposure to the study drug, and
- the event is a known reaction to the study drug that cannot be explained by an alternative cause commonly occurring in the population/individual, or
- the event is not a known reaction to the study drug but cannot be reasonably explained by an alternative cause.

Possible: Adverse events that, after careful medical evaluation, do not meet the criteria for a definite or probable relationship to the study drug, but for which a connection cannot be ruled out with certainty. The following characteristics will apply:

- · the event occurs after exposure to the study drug, and
- there is a reasonable temporal relationship to the application, but the event is not a known reaction to the study drug and could be explained by a commonly occurring alternative cause, or
- in the absence of a reasonable temporal relationship, the event cannot be explained by an alternative cause.

Not related: Adverse events in this category will have either of the following characteristics:

• the event does not have a reasonable temporal relationship to study drug administration and/or can be explained by a commonly occurring alternative cause.

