2. OBJECTIVES

The objective is to assess the safety of repeat IT injections of 12 mg OTO-104 at 3-month intervals in an open-label study in subjects with unilateral Meniere's disease.

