6. DOSAGE AND ADMINISTRATION

6.1. Study Drug Administration

OTO-104 12 mg will be administered as a single, 0.2 mL intratympanic injection of 60 mg/mL OTO-104. The recommended injection procedure for intratympanic administration of OTO-104 in Meniere's disease subjects is as follows:

- 1. Place the subject in a recumbent position with the treated ear upwards. Anesthetize the tympanic membrane by covering the external surface of the posterior inferior quadrant with topical lidocaine/prilocaine cream (i.e., _______) until the tympanic membrane is numb. If applicable, suction away the topical lidocaine/prilocaine cream.
- 2. Using the 1 mL syringe pre-loaded with OTO-104 and equipped with a 25 or 26 gauge needle, insert the needle through the tympanic membrane with the bevel facing in an inferoposterior direction to a depth of approximately 2-3 mm just inferior to the round window niche, and with firm but gentle pressure, inject 0.2 mL taking care not to insert the needle further than necessary. Use of this technique will minimize the possibility of OTO-104 adhering to the underside of the tympanic membrane. Do not incise the tympanic membrane to form a ventilation hole as this is not needed due to the small injection volume.

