11.7.1. Adverse Events

Version 18.1 of Medical Dictionary for Regulatory Activities (MedDRA) will be used to code all AEs.

The primary analysis of AEs will consider only treatment emergent AEs (TEAEs), events occurring for the first time, or worsening during or after the first dose of study drug. Subject incidence of TEAEs and SAEs will be tabulated by preferred terms and system organ class. These analyses may also be tabulated by visit, time of onset and/or cumulative exposure. In addition, severity and relationship to study drug will also be presented. Adverse events will be presented by descending order of frequency in MedDRA system organ class and preferred term.

Subgroup analyses of AEs by gender will be examined. Listings of all SAEs, AEs leading to study withdrawal, and deaths on-study will also be included. Duration and outcome of each AE will be reported in subject listings.

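### AE causality is rated and tabulated against the study drug only, although the objective is the safety of repeat intratympanic injections, and the status of the injection procedure as a cause is left open

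*Combined protocol and SAP*

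**What the plan says.** The objective in Section 2 is to "assess the safety of repeat IT injections of 12 mg OTO-104 at 3-month intervals". Section 6.1 describes what each injection involves: the eardrum is numbed with a lidocaine/prilocaine cream, and the operator must then "insert the needle through the tympanic membrane with the bevel facing" as specified.

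Section 9.1.2 defines the causality rating: "The investigator will assess the relationship or association of the study drug in causing or contributing to the AE". It has four levels: *Definite*, *Probable*, *Possible* and *Not related*. *Definite* requires that "other conditions (concurrent illness, progression/expression of disease state, or concurrent medication reaction) do not appear to explain the event". *Not related* applies where "the event does not have a reasonable temporal relationship to study drug administration and/or can be explained by a commonly occurring alternative cause".

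Section 11.7.1 makes all TEAEs the primary AE analysis and adds that "severity and relationship to study drug will also be presented". Section 9.2.1 uses both study drug and study therapy for the target of the investigator's opinion, and defines neither as including or excluding the procedure.

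**The concern.** The question asked is about injections, while the attribution is about the drug. Ear pain on the day of dosing, vertigo during the injection or otitis media a few days later could come from the needle, the anesthetic cream, the injected volume or dexamethasone. The only attribution the plan commits to for AEs is the investigator's rating, and no second item records a relationship to the procedure.

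The study has one open-label group and no sham or vehicle injection, so no between-group comparison can separate drug from procedure. That puts more weight on the rating. If sites differ on whether the needle is part of the study drug or a competing explanation, the related-AE count partly reflects how they read the form. Where the procedure is read as a competing explanation, the count understates injection-related risk.

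**Working it through.** The plan gives no figure on this point, so there is none to reproduce. The check is a reading of the definitions against one another, followed by what they imply for the tables.

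**1. Is the procedure a rating target anywhere?** Sections 9, 9.1.2, 9.2.1 and 11.7.1 all name the study drug. Section 9.2.1 also says study therapy, a broader but undefined term. In 9.1.2, drug administration and application appear only as reference points for timing. No section asks for a relationship to the puncture or the anesthetic.

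**2. What ratings does the text allow for one event?** Take ear pain that starts at the injection and that the investigator attributes to the needle.

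- *Not related*: the and/or in the definition means that an event which "can be explained by a commonly occurring alternative cause" qualifies even when the timing fits. An investigator who regards the needle as such a cause may choose this level.
- *Possible*: this level covers an event with fitting timing that is not a known drug reaction and could have a common alternative explanation. The same event fits here too, because the two definitions overlap.
- *Probable* or *Definite*: an investigator who regards the injection as part of receiving the drug sees no competing cause. The examples given under *Definite* are illness, disease and other medication, and do not include the procedure.

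Nothing in 9.1.2 chooses between these readings.

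**3. How many people apply the definitions?** Section 4.1 plans up to 300 subjects at about 60 to 70 sites. That is at most 300 × 2 = 600 injections, and on average between 300/70 ≈ 4.3 and 300/60 = 5 subjects per site. Many raters would each apply their own reading to a handful of subjects.

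**4. What happens to the tables?** Let *I* be the number of subjects whose only potentially related event is injection-caused, *s* the share of them rated *Not related*, and *R* the number of subjects with any other related event.

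- Related count = *R* + (1 − *s*) × *I*
- Subjects with any TEAE: unchanged for every value of *s*

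The documents give neither *I* nor *s*, and *s* can lie anywhere from 0 to 1. At *s* = 0 nothing is lost. At *s* = 1 all *I* subjects drop out of the related count. The direction is downward, and the size is unknown.

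**5. What does not depend on the rating?**

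- TEAE and SAE incidence by system organ class and preferred term (11.7.1).
- The sponsor's periodic review of all AEs in the ear and labyrinth class (14.7).
- Otoscopy and audiometry, tabulated separately for the treated and untreated ear (11.7.3, 11.7.4).
- Eardrum perforations that do not enlarge, or that resolve by study end. Sections 8.2.5 and 9 keep these out of AE reporting, so they never reach the causality item and are seen through otoscopy.

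**The case against.** The best defence is that the under-counting reading is the less natural one. A puncture required by the protocol, made only to deliver the product, is an odd example of a commonly occurring alternative cause. The *Probable* definition ties such causes to the population or the individual. The causes listed under *Definite* leave the procedure out, which suggests that it belongs to the exposure, and study therapy in 9.2.1 points the same way. Causality also decides nothing about what is reported, and total TEAE incidence already describes drug and injection together, as the objective asks. The eCRF, its completion guidelines and the separate SAP are not in the available text and may contain a procedure item.

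Much of this stands. A reader might infer that needle-caused events must be rated *Not related*. The text permits that but does not require it. A reader might also infer that the plan has no other evidence on local injection safety. The comparison of treated with untreated ears in otoscopy and audiometry is such evidence. Nor is attribution wholly lost afterwards: event descriptions and onset dates are collected, so events close to dosing could be partly reclassified, though not with the investigator's judgement at the time.

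What the defence does not supply is a sentence that settles the reading. Even on the favourable reading, drug and procedure would be merged in one rating. If a procedure item exists in the eCRF, 9.1.2 and 11.7.1 still need to be aligned with it.

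**Conclusion.** The point holds in a limited form. The causality rating and its table address the study drug, the objective addresses repeat injections, and the definitions let sites place the same injection-caused event at different levels. Only the relatedness table and statements drawn from it are affected. The main safety result, which is the incidence of all TEAEs and SAEs, is not.

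A reader might want to put a number on this. If 5% to 20% of 300 subjects had an injection-procedure event, 300 × 0.05 = 15 to 300 × 0.20 = 60 subjects could move between related and *Not related*. The documents do not support that as an estimate. The rate is assumed, 300 is a maximum, and the figure treats every such subject as open to either rating with no other related event. It is an upper bound on an assumption, so the number affected should be reported as unknown.

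The conclusion assumes that no document outside the available text already defines the procedure's place in the rating.

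**What to change.** Four changes:

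1. In 9.1.2, state that the injection procedure, including the topical anesthetic, is not an alternative cause that supports *Not related*.
2. Add a causality item for relationship to the injection procedure, on the same four levels.
3. In 9.1.2 and 9.2.1, use one defined term in place of study drug and study therapy.
4. In 11.7.1, tabulate TEAEs related to drug, related to procedure, and related to either. The last of these matches the objective and is the least sensitive to how an investigator divides an event between needle and drug.

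The cost is a short text change, one more eCRF field and one more table, with no added visit or assessment. The related-AE rate is likely to look somewhat less favourable. The split between drug and procedure will remain a matter of judgement in a single-arm study, and the report should say so.
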